**Table 1. Stopping rule for safety**

Stop, if there are this many patients who do not	2	3	4	5	6
--	---	---	---	---	---

complete cumulative cisplatin dose of 200 mg/m 					
In this many patients	2-4	5-7	8-10	11-13	14-16

## 6 Study Procedures and Schedule of Events

The study-specific procedures and assessments are detailed in this section and outlined in the Study Calendar – Section 6.1.

Screening assessments must be performed within 28 days prior to the first dose of investigational product, unless otherwise noted. Any results falling outside of the reference ranges may be repeated at the discretion of the investigator.

Audiogram will be obtained following the institutional standards and will include air-conduction thresholds at (minimally) octave intervals from 0.25 to 8 kHz.

All on-study visit procedures are allowed a **window of  $\pm$  2 days** unless otherwise noted. Treatment or visit delays for public holidays or weather conditions do not constitute a protocol violation.

## 6.1 Study Calendar

### Weekly cisplatin

Period/Procedure	Screening	Cycle 1 and Future Cycles								End of Treatment	Long Term/Survival Follow 
Study Day/ Visit Day	-28	1 (+/- 2 days)	8 (+/- 2 days)	15 (+/- 2 days)	22 (+/- 2 days)	29 (+/- 2 days)	36 (+/- 2 days)	43*  (+/- 2 days)	133 (+/- 30 days)	Every 3 months (+/- 30 days)	
Study Treatment/Drug Administration											
Cisplatin		X	X	X	X	X	X	X			
Sodium Thiosulfate		X	X	X	X	X	X	X			
Clinical Assessments											
Physical exam	X	X	X	X	X	X	X	X	X		
Medical history	X										
Vital signs	X	X	X	X	X	X	X	X	X		
Concomitant medications	X	X	X	X	X	X	X	X	X		
AE assessment		X	X	X	X	X	X	X	X		

Long Term/Survival Follow-up will occur every 3 months via telephone calls up to 36 months.

 Day 43 can be omitted at the discretion of treating physician

Period/Procedure	Screening	Cycle 1 and Future Cycles								End of Treatment	Long Term/Survival Follow-Up 
Study Day/ Visit Day	-28	1 (+/- 2 days)	8 (+/- 2 days)	15 (+/- 2 days)	22 (+/- 2 days)	29 (+/- 2 days)	36 (+/- 2 days)	43*2 (+/- 2 days)	133 (+/- 30 days)	Every 3 months (+/- 30 days)	
Disease assessment 	x										
Performance status	x	x	x	x	x	x	x	x	x		
Audiogram	x								x		
Survival/Long-term Follow-up										x	
Questionnaires											
HHIA-S	x				x				x		
*PRO-CTCAE	x				x§ 				x		
Laboratory Assessments											
Hematology 	x	x	x	x	x	x	x	x	x		
Chemistry 	x	x	x	x	x	x	x	x	x		

 Documentation of disease assessment using AJCC Cancer Staging Manual 8th edition §PRO-CTCAE can be obtained between days 14 and 23 Including CBC with differential and platelet count Including alkaline phosphatase (ALP), aspartate aminotransferase/alanine aminotransferase (ALT/AST), total bilirubin, calcium, phosphorus, blood urea nitrogen (BUN), creatinine, total protein, albumin, glucose, potassium, sodium, chloride, bicarbonate

Period/Procedure	Screening	Cycle 1 and Future Cycles							End of Treatment	Long Term/Survival Follow-Up 
Study Day/ Visit Day	-28	1 (+/- 2 days)	8 (+/- 2 days)	15 (+/- 2days)	22 (+/- 2 days)	29 (+/- 2 days)	36 (+/- 2 days)	43* (+/- 2 days)	133 (+/- 30 days)	Every 3 months (+/- 30 days)
Urine pregnancy test 	x									

---

 For women of child-bearing potential must have a negative urine pregnancy at screening.

**High dose Q3W cisplatin group**

Period/Procedure	Screening	Cycle 1 and Future Cycles								End of Treatment	Long Term/Survival Follow-Up 
Study Day/ Visit Day	-28	1 (+/- 2 days)	8 (+/- 2 days)	15 (+/- 2 days)	22 (+/- 2 days)	29 (+/- 2 days)	36 (+/- 2 days)	43 *2 (+/- 2 days)	133 (+/- 30 days)	Every 3 months (+/- 30 days)	
Study Treatment/Drug Administration											
Cisplatin		X			X			X			
Sodium Thiosulfate		X			X			X			
Clinical Assessments											
Physical exam	X	X			X			X	X		
Medical history	X										
Vital signs	X	X			X			X	X		
Concomitant medications	X				X			X	X		
AE assessment		X			X			X	X		
Disease assessment 	X										

 Long Term/Survival Follow-up will occur every 3 months via telephone calls up to 36 months. Day 43 can be omitted at the discretion of treating physician Documentation of disease assessment using AJCC Cancer Staging Manual 8th edition

Period/Procedure	Screening	Cycle 1 and Future Cycles							End of Treatment	Long Term/Survival Follow-Up 
Study Day/ Visit Day	-28	1 (+/- 2 days)	8 (+/- 2 days)	15 (+/- 2 days)	22 (+/- 2 days)	29 (+/- 2 days)	36 (+/- 2 days)	43*2 (+/- 2 days)	133 (+/- 30 days)	Every 3 months (+/- 30 days)
Performance status	x	x			x			x	x	
Audiogram	x								x	
Survival/Long-term Follow-up										x
Questionnaires										
HHIA-S	x				x				x	
*PRO-CTCAE	x				x§ 				x	
Laboratory Assessments										
Hematology 	x	x			x			x	x	
Chemistry 	x	x			x			x	x	
Urine pregnancy test 	x									

 §PRO-CTCAE can be obtained between days 14 and 23 Including CBC with differential and platelet count Including alkaline phosphatase (ALP), aspartate aminotransferase/alanine aminotransferase (ALT/AST), total bilirubin, calcium, phosphorus, blood urea nitrogen (BUN), creatinine, total protein, albumin, glucose, potassium, sodium, chloride, bicarbonate For women of child-bearing potential must have a negative urine pregnancy at screening.

## 6.2 Participant Registration

A written, signed, informed consent form (ICF) and a Health Insurance Portability and Accountability Act (HIPAA) authorization must be obtained before any study-specific assessments are initiated. A copy of the signed ICF will be given to the subject and a copy will be filed in the medical record. The original will be kept on file with the study records.

All participants consented to the study will be registered in OnCore®, the UCSF Helen Diller Family Comprehensive Cancer Center Clinical Trial Management System (CTMS). The system is password protected and meets HIPAA requirements.

## 6.3 Schedule of Procedures and Assessments

### 6.3.1 Pretreatment Period

#### 6.3.1.1 Screening Assessments

The Screening procedures and assessments must be completed within 28 days of initiating study treatment.

- Clinical Assessments
  - Documentation of disease assessment using AJCC Cancer Staging Manual 8th edition
  - Physical examination
  - Complete medical history
  - Vital signs
  - Concomitant medication review
  - Performance status
  - Audiologic assessments including audiogram
  - Questionnaires
    - A questionnaire based on PRO-CTCAE for selected oral, GI, neurologic and perceptual symptoms (dry mouth, difficulty swallowing, mouth/throat sores, taste changes, nausea, vomiting, numbness & tingling, and ringing in ears)
    - Hearing Handicap Inventory for Adults – Screening (HHIA-S)
- Laboratory Assessments
  - Hematology labs - CBC with differential and platelet count
  - Blood chemistry assessment, including: Alkaline phosphatase (ALP), aspartate aminotransferase/alanine aminotransferase (ALT/AST), total bilirubin, calcium, phosphorus, blood urea nitrogen (BUN), creatinine, total protein, albumin, glucose, potassium, sodium, chloride, bicarbonate
  - Urine Pregnancy Test - For women of child-bearing potential.

### 6.3.2 Treatment Period

#### 6.3.2.1 Study Procedures on treatment days

- Clinical Assessments
  - Physical examination
  - Vital signs
  - Concomitant medication review
  - AE assessment
  - Performance status
  - Questionnaires (On Day 22 only)
    - A questionnaire based on PRO-CTCAE for selected oral, GI, neurologic and perceptual symptoms (dry mouth, difficulty swallowing, mouth/throat sores, taste changes, nausea, vomiting, numbness & tingling, and ringing in ears)
    - Hearing Handicap Inventory for Adults – Screening (HHIA-S)
- Laboratory Assessments (Days 1, 8, 15, 22, 29, 36 for subjects getting weekly cisplatin and days 1 and 22 for subjects getting every-3-week cisplatin Day 43 labs will only be collected if treatment occurs that day).
  - Hematology labs - CBC with differential and platelet count
  - Blood chemistry assessment, including: Alkaline phosphatase (ALP), aspartate aminotransferase/alanine aminotransferase (ALT/AST), total bilirubin, calcium, phosphorus, blood urea nitrogen (BUN), creatinine, total protein, albumin, glucose, potassium, sodium, chloride, bicarbonate
- Treatment with cisplatin and sodium thiosulfate

### 6.3.3 Post-treatment/Follow-Up

Participants will be followed at least once around 3 months +/- 2 weeks after discontinuing study treatment. The following procedures will be performed at the Follow Up visit:

- Clinical Assessments
  - Physical examination
  - Vital signs
  - Concomitant medication review
  - AE assessment
  - Performance status
  - Audiologic assessments including audiogram
  - Questionnaires
    - A questionnaire based on PRO-CTCAE for selected oral, GI, neurologic and perceptual symptoms (dry mouth,

- difficulty swallowing, mouth/throat sores, taste changes, nausea, vomiting, numbness & tingling, and ringing in ears)
- Hearing Handicap Inventory for Adults – Screening (HHIA-S)
- Laboratory Assessments
  - Hematology labs - CBC with differential and platelet count
  - Blood chemistry assessment, including: Alkaline phosphatase (ALP), aspartate aminotransferase/alanine aminotransferase (ALT/AST), total bilirubin, calcium, phosphorus, blood urea nitrogen (BUN), creatinine, total protein, albumin, glucose, potassium, sodium, chloride, bicarbonate

### 6.3.4 Long Term/Survival Follow-up

After completing the follow-up period, participants can be contacted by telephone every 3 months (+/- 30 days) up to 3 years to assess for event free survival and overall survival after initiation of treatment to confirm that there is no reduced efficacy of cisplatin when administered prior to sodium thiosulfate (STS) and to assess for survival/anti-cancer therapy status until death, withdrawal of consent, or the end of the study, whichever occurs first.

## 6.4 Use of Concurrent/Concomitant Medications

Participants should receive anti-emetic therapy based on UCSF guidelines at the treating physician's discretion. Use of growth factors is not allowed for patients getting weekly cisplatin , but can be allowed at the treating physician's discretion for patients getting every-3-week cisplatin.

## 7 Reporting and Documentation of Results

### 7.1 Evaluation of Safety

#### 7.1.1 Definitions

##### **Evaluable for toxicity**

All participants will be evaluable for toxicity from the time of their first treatment with sodium thiosulfate.

#### 7.1.2 Evaluation of Safety

The safety parameters for this study include all laboratory tests and hematological abnormalities, physical findings, and spontaneous reports of adverse events reported to the investigator by participants.

Toxicity will be assessed according to the NCI CTCAE version 5.0. Safety analyses will be performed for all participants who received at least one dose of sodium thiosulfate.

## 7.2 Definitions of Adverse Events

### 7.2.1 Adverse Event

An adverse event (also known as an adverse experience) is defined as any untoward medical occurrence associated with the use of a drug in humans, whether or not considered drug related. More specifically, an adverse event (can be any unfavorable and unintended sign (e.g., an abnormal laboratory finding), symptom, or disease temporally associated with the use of a drug, without any judgment about causality. An adverse event can arise from any use of the drug (e.g., off-label use, use in combination with another drug) and from any route of administration, formulation, or dose, including an overdose.

### 7.2.2 Adverse Reaction

An adverse reaction is defined as any adverse event caused by the use of a drug. Adverse reactions are a subset of all suspected adverse reactions for which there is reason to conclude that the drug caused the event.

### 7.2.3 Suspected Adverse Reaction

A suspected adverse reaction is defined as any adverse event for which there is a reasonable possibility that the drug caused the adverse event. For the purposes of IND safety reporting, “reasonable possibility” indicates that there is evidence to suggest a causal relationship between the drug and the adverse event. A suspected adverse reaction implies a lesser degree of certainty about causality than an adverse reaction.

#### 7.2.3.1 Unexpected

An adverse event or suspected adverse reaction is considered *unexpected* if it is not listed in the investigator brochure or package insert(s), or is not listed at the specificity or severity that has been observed, or, if an investigator brochure is not required or available, is not consistent with the risk information described in the general investigational plan or elsewhere in the current application.

“Unexpected,” as used in this definition, also refers to adverse events or suspected adverse reactions that are mentioned in the investigator brochure as occurring with a class of drugs or as anticipated from the pharmacological properties of the drug, but are not specifically mentioned as occurring with the particular drug under investigation.

Adverse events that would be anticipated to occur as part of the disease process are considered *unexpected* for the purposes of reporting because they would not be listed in the investigator brochure. For example, a certain number of non-acute deaths in a cancer trial would be anticipated as an outcome of the underlying disease, but such deaths would generally not be listed as a suspected adverse reaction in the investigator brochure.

Some adverse events are listed in the Investigator Brochure as occurring with the same class of drugs, or as anticipated from the pharmacological properties of the drug, even though they have not been observed with the drug under investigation. Such events would be considered *unexpected* until they have been observed with the drug under investigation. For example, although angioedema is anticipated to occur in some participants exposed to drugs in the angiotensin-converting enzyme inhibitor class and angioedema would be described in the investigator brochure as a class effect, the first case of angioedema observed with the drug under investigation should be considered *unexpected* for reporting purposes.

### 7.2.3.2 Serious

An adverse event or suspected adverse reaction is considered *serious* if, in the view of either the investigator or sponsor, it results in any of the following outcomes:

- Death
- Life-threatening adverse event
- Inpatient hospitalization or prolongation of existing hospitalization
- A persistent or significant incapacity or substantial disruption of the ability to conduct normal life function
- Congenital anomaly/birth defect

Important medical events that may not result in death, are life-threatening, or require hospitalization may be considered serious when, based upon appropriate medical judgment, they may jeopardize the participant and may require medical or surgical intervention to prevent one of the outcomes listed in this definition. Examples of such medical events include allergic bronchospasm requiring intensive treatment in an emergency room or at home, blood dyscrasias or convulsions that do not result in inpatient hospitalization, or the development of drug dependency or drug abuse.

### 7.2.3.3 Life-threatening

An adverse event or suspected adverse reaction is considered life-threatening if, in the view of either the investigator or sponsor, its occurrence places the participant at immediate risk of death. It does not include an adverse event or suspected adverse reaction that, had it occurred in a more severe form, might have caused death.

## 7.2.4 Recording of Adverse Events

Refer to the Data Safety Monitoring Plan, located in Appendix 2.

## 7.2.5 Follow-up of Adverse Events

All participants who experience adverse events will be followed with appropriate medical management until resolved or stabilized, as determined by the investigator, or until the initiation of new anti-cancer therapy, whichever occurs first. For selected adverse events for which administration of the investigational product was stopped, a re-challenge of the subject with the investigational drug may be conducted if considered both safe and ethical by the investigator.

## 7.2.6 Adverse Events Monitoring

Refer to the Data Safety Monitoring Plan, located in Appendix 2.

## 7.2.7 Expedited Reporting

### Reporting to the Data and Safety Monitoring Committee

If a death occurs during the treatment phase of the study or within 30 days after the last administration of the study drug(s) and it is determined to be related either to the study drug(s) or to a study procedure, the Investigator or his/her designee must notify the DSMC Chair (or qualified alternate) within 1 business day of knowledge of the event. The contact may be by phone or e-mail.

### Reporting to Institutional Review Board

The UCSF PI must report events to the UCSF IRB according to institutional guidelines.

UCSF IRB website for guidance in reporting adverse events: <https://irb.ucsf.edu/adverse-event>

### **Expedited Reporting to the FDA**

If the study is being conducted under an IND, the Sponsor (or the Sponsor-Investigator) is responsible for determining whether or not the suspected adverse reaction meets the criteria for expedited reporting in accordance with federal regulations (21 CFR §312.32).

The Sponsor (or Sponsor-Investigator) must report in an IND safety report any suspected adverse reaction that is both serious and unexpected. The Sponsor needs to ensure that the event meets all three definitions:

- Suspected adverse reaction
- Unexpected
- Serious

If the adverse event does not meet all three of the definitions, it should not be submitted as an expedited IND safety report.

The timeline for submitting an IND safety report to FDA is no later than **15 calendar days** after the Investigator determines that the suspected adverse reaction qualifies for reporting (21 CFR 312.32(c)(1)).

Any unexpected fatal or life-threatening suspected adverse reaction will be reported to FDA no later than **7 calendar days** after the Investigator's initial receipt of the information (21 CFR 312.32(c)(2)).

Any relevant additional information that pertains to a previously submitted IND safety report will be submitted to FDA as a Follow-up IND Safety Report without delay, as soon as the information is available (21 CFR 312.32(d)(2)).

## **8 Statistical Considerations and Analysis Plan**

Feasibility will be evaluated as the successful completion of 5 weekly cisplatin or 2 every-3-week cisplatin without any extended treatment related delays more than 7 days by at least 75% of patients. Safety will be measured by:

- Frequency of drug related adverse events occurring up to 7 days after the last dose of STS
- Frequency of serious adverse events occurring up to 7 days after the last dose of STS
- Frequency of clinical laboratory test abnormalities by worst toxicity grade using NCI CTCAE version 5.0

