## Abstract

Title	A Phase II study of Sodium thiosulfate (STS) for prevention of ototoxicity in patients with locally advanced squamous cell carcinoma of head and neck (SCCHN) undergoing concurrent chemoradiation with cisplatin
Study Description	This is a phase II study to establish feasibility of using sodium thiosulfate after intravenous cisplatin in head and neck cancer patients undergoing definitive concurrent chemoradiation for prevention of ototoxicity. Hypothesis is that use of intravenous STS would be feasible and safe in patients with locally advanced SCCHN undergoing concurrent chemoradiation with cisplatin. This is a prospective clinical trial for patients getting either weekly cisplatin (40mg/m  ) or every-3-week cisplatin (100mg/m  ). A total of 16 patients will be enrolled and each subject will have baseline and post-treatment (3 months after the completion of concurrent chemoradiation) audiogram to assess hearing loss as defined by NCI CTCAE version 5.0. STS (10 g/m  for weekly cisplatin group and 20g/m  for high dose cisplatin group) will be infused 4 hours after each cisplatin infusion is completed. Feasibility will be assessed by successful completion of planned treatment, defined by completion of 5 weekly cisplatin or 2 high dose cisplatin without any extended treatment related delays more than > 7 days.
Phase of Study	Phase II Study
Investigational Products	Sodium thiosulfate (STS)
Study population	Patients with locally advanced SCCHN (oral cavity, oropharynx, hypopharynx, and larynx) eligible for definitive concurrent chemoradiation with cisplatin would be eligible for the study. Patients must be at least 18 years old at the time of enrollment. Women and persons from ethnic minority groups are encouraged to participate the study.
Primary Objective	Primary objective is to establish feasibility of intravenous STS after each dose of concurrent cisplatin in patients with locally advanced head and neck squamous cell carcinoma undergoing definitive radiotherapy.

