### 1.4 Rationale for the Dose Selection/Regimen

Intravenous STS 10 g/m^2 or 20 g/m^2 will be administered over 1-2 hours, 4 hours after each cisplatin dose is completed, depending on weekly or high dose cisplatin regimen. In recent clinical trials in pediatric cancer patients, STS 20 g/m^2 infused after 6 hours of cisplatin has been well tolerated with little compromise in oncologic outcome. STS can reduce toxicities from cisplatin by quenching reactive oxygen species, preserving the activity of antioxidant enzymes, and forming biologically inactive complexes with cisplatin to effectively reduce the systemic exposure to cisplatin. In pediatric hepatoblastoma study, STS 20 g/m^2 was given after cisplatin 80mg/m^2. For lower dose, weekly cisplatin, 10g/m^2 would be reasonable, as only half dose of cisplatin (40mg/m^2) is given. In animal studies, STS given 4 hours after cisplatin was able to protect rats from ototoxicity with minimal compromise in anti-tumor activity of cisplatin, whereas STS 8 and 12 hours after cisplatin had less and no protective effects at all [13]. STS is a FDA approved agent for treatment of cyanide poisoning and it is approved to be given as a single dose of 12.5g after infusion of 300mg of sodium nitrite. In a phase 3 trial for calciphylaxis, STS is given 25 g per day for 3 times a week[14].

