### 2.2 Primary Objective and Endpoint

Primary Objective	Endpoint	Time Frame
To establish feasibility of intravenous STS after each dose of concurrent cisplatin in patients with locally advanced head and neck squamous cell carcinoma undergoing definitive radiotherapy.	Feasibility measured by successful completion of planned treatment, defined by completion of at least 5 weekly cisplatin or 2 high dose cisplatin administrations without extended treatment related delays more than 7 days.	Occurring up to 7 days after the last dose of STS

[figure not shown]

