### 3.2 Sample Size

Target accrual is a total of 16 patients, and to account for screen failures and withdrawals, we will consent up to 18 patients. Patients can be enrolled to the and can get concurrent chemoradiation with weekly cisplatin (40 mg/m^2) given once a week or concurrent chemoradiation with high dose cisplatin (80-100 mg/m^2) given every 3 weeks. Participants who do not receive any dose of STS will not be evaluable and will be replaced.

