## 5.4 Stopping Rules

We will use Bayesian decision rules for the study to decide respectively early stop out of safety or feasibility concerns. We expect that at least 75% of patients would receive target cumulative cisplatin dose of 200 mg/m^2 which is similar for both weekly and high dose cisplatin groups[15]. We assume that no more than 25% of patients would fail to receive cumulative cisplatin dose of 200 mg/m^2 in either cisplatin dose stratum. With the Beta prior distribution with parameters 2 and 6, the prior expected rate is set at the targeted rate of 25%, and the prior probability of the risk greater than 25% is 45%. We apply this prior distribution to the observed number of patients experiencing high grade toxicity and compute the posterior (updated) probability of the risk of such toxicities greater than 25%. In each cisplatin dose stratum we will consider stopping treatment any time if the posterior probability is at least .70(Table 1).

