## 8.4 Analyses Plans

We will report the proportion of patients experiencing high-grade toxicity with exact binomial 95% confidence intervals. We will also describe patient experiences with respect to feasibility as defined above. All other adverse events will be similarly summarized by type and grade.

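### The 75% feasibility criterion and the toxicity proportion are stated over all 16 patients, so a pass does not show that each STS regimen is feasible

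*Combined protocol and SAP*

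**What the plan says.** Patient-level success in Section 2.2 is "completion of at least 5 weekly cisplatin or 2 high dose cisplatin administrations without extended treatment related delays more than 7 days". Section 8 turns this into a trial-level criterion, completion "without any extended treatment related delays more than 7 days by at least 75% of patients", and names no regimen or STS dose. Section 8.4 says "We will report the proportion of patients experiencing high-grade toxicity with exact binomial 95% confidence intervals" and then promises a description of feasibility. It splits neither by regimen.

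Two regimens are given. Section 1.4 sets STS at 10 or 20 g/m2 "depending on weekly or high dose cisplatin regimen". Table 5.1 pairs 10 g/m2 with cisplatin 40 mg/m2 weekly, and 20 g/m2 with cisplatin 80-100 mg/m2 every 3 weeks. Section 3.2 says "Target accrual is a total of 16 patients" and allows either regimen, with no quota, minimum or ratio.

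Elsewhere the plan does separate the regimens. Section 5.4, which covers both safety and feasibility concerns, says "In each cisplatin dose stratum we will consider stopping treatment any time if the posterior probability is at least" 0.70. All four secondary endpoints in Section 2.3 are reported by cohort. The primary endpoint row in Section 2.2 has no such wording.

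**The concern.** Section 1.3 intends a promising result to support a larger study, so readers need to know which regimen the result supports. The regimens differ twofold in STS per infusion and 2- to 2.5-fold in cisplatin per dose. With no fixed mix, most patients could be on one regimen, and a criterion taken over everyone would then mainly describe that regimen. A single toxicity proportion would also average over any difference between the two STS doses. The final criterion and the stratum stopping rule could point in opposite directions, and the plan does not say which governs the conclusion.

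**Working it through.** **Inputs.** N = 16 (Section 3.2); threshold 75% (Section 8); prior Beta(2, 6), cut-off 0.70 and failure limit 25% (Section 5.4); boundary of 2 failures in 2-4 patients (Table 1). The number k on the every-3-week regimen is not given, so it is varied. True success rates by regimen are not given either; 90% (weekly) and 40% (every 3 weeks) are assumptions for illustration.

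**1. The plan's own figures.**
- Prior: the mean is 2/8 = 0.25 and P(risk > 0.25) = 0.445, agreeing with the stated 45%.
- Boundary: with x failures in n patients the posterior is Beta(2 + x, 6 + n - x). For x = 2, P(risk > 0.25) is 0.834 (n = 2), 0.776 (n = 3) and 0.713 (n = 4). All exceed 0.70, so the first column of Table 1 reproduces.
- Margin of error in Section 8.2: 1.96 x sqrt(0.5 x 0.5 / 16) = 0.245, not the stated 0.345. With n = 8 the same formula gives 0.346. This is a separate matter, taken up below only as evidence of intent.

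**2. What the criterion tolerates.** 0.75 x 16 = 12 successes are needed, so 4 failures are allowed. If all k patients at 20 g/m2 fail and all others succeed, the pooled rate is (16 - k)/16:

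| k | Pooled rate | Criterion |
|---|---|---|
| 1 | 15/16 = 93.8% | met |
| 2 | 14/16 = 87.5% | met |
| 3 | 13/16 = 81.3% | met |
| 4 | 12/16 = 75.0% | met |
| 5 | 11/16 = 68.8% | not met |

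At k = 4 the stratum result is 0/4, with exact 95% interval 0 to 0.60. That interval excludes 75%, yet the trial criterion is met.

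**3. How often the two answers differ, under the assumed rates.**
- Pooled pass = sum over a + b >= 12 of Bin(a; 16 - k, 0.9) x Bin(b; k, 0.4).
- Stratum pass = P(Bin(k, 0.4) >= m), with m the smallest whole number not below 0.75k.
- Early stopping is ignored in both.

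| Weekly / every 3 weeks | Pooled pass | m | Stratum reaches 75% |
|---|---|---|---|
| 14 / 2 | 0.92 | 2 | 0.16 |
| 12 / 4 | 0.75 | 3 | 0.18 |
| 10 / 6 | 0.48 | 5 | 0.04 |
| 8 / 8 | 0.25 | 6 | 0.05 |

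**4. Whether Section 5.4 closes the gap.** Table 1 counts patients who fall short of 200 mg/m2 cumulative cisplatin. Section 8 also fails a patient for a treatment-related delay over 7 days, which Table 1 does not count. The definitions also part on dose: two administrations at 80 mg/m2 total 160 mg/m2, which meets the Section 8 count but falls short under Section 5.4. Those passages must be reconciled. Finally, nothing carries a met boundary into Section 8. Two shortfalls in the first two every-3-week patients meet the boundary (posterior 0.834), yet if the other 14 patients are weekly successes the pooled result is 14/16 = 87.5%.

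**The case against.** The strongest reply is that feasibility is not judged by the 75% criterion alone. Section 5.4 applies a matching 25% failure limit within each stratum. If every failure is a dose shortfall, 0/4 meets the boundary at the second patient. In the 12/4 illustration, the chance of at least 2 failures in 4 is 0.82, the complement of 0.18, so every case in which those four miss 75% would be flagged. This stands as mitigation. It does not cover failures by delay alone, it only prompts consideration of stopping, and it does not alter the final criterion.

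Section 8 also never uses the word pooled, and the 0.345 margin fits about 8 patients, which might hint at estimation by stratum. It might equally be a slip for 0.245. Intent is unclear, which is a reason to write it down.

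Combining regimens is defensible in a 16-patient study seeking preliminary evidence. STS is scaled to cisplatin, and planned cumulative STS is similar (7 x 10 = 70 against 3 x 20 = 60 g/m2). That supports keeping a pooled figure, but not relying on it alone. Section 8.4 does not bar tables by regimen; it simply does not promise them.

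A reader might infer that the plan lets 20 g/m2 be declared feasible after total failure at any mix. The documents do not support that: with 5 or more such patients all failing, the criterion cannot be met. Nor do they say that a stopped stratum's places go to weekly patients. Section 3.2 provides only for replacing participants who receive no STS.

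**Conclusion.** The point holds in a limited form. As written, the primary criterion and the toxicity proportion cover all patients, no mix is fixed, and no rule says what a pass means for either regimen. A pass with every 20 g/m2 patient failing is arithmetically possible only with at most 4 of 16 on that regimen. It is an extreme case: under the assumed rates, 12/12 with 0/4 has probability 0.9^12 x 0.6^4 = 0.037. The more general problem is the gap between the pooled and stratum answers (0.75 against 0.18 at 12/4). Its size rests on the assumed 90% and 40% rates and on the mix: the pooled pass falls to 0.25 at 8/8, although the stratum figure there is only 0.05. Section 5.4 narrows the gap, mainly for dose shortfalls, but leaves the trial able to meet its feasibility criterion while one stratum has met its feasibility stopping boundary. This should be settled before analysis; it does not invalidate the design.

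**What to change.** In Sections 8 and 8.4:

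- Report feasibility and high-grade toxicity by regimen started (STS 10 g/m2 weekly, STS 20 g/m2 every 3 weeks), each with an exact 95% interval, beside the pooled figure.
- Identify patients who switched to weekly cisplatin under Section 5.2.5, and state how feasibility success is counted for them, since regimen started alone does not describe what they received.
- State the feasibility conclusion per regimen.
- State that a regimen whose stratum met the Section 5.4 boundary will not be described as feasible on the strength of the pooled proportion.
- State how remaining places are filled if a stratum stops.

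This needs analysis-plan wording and extra table columns, with no additional patients. The price is wide per-regimen intervals (0/4 gives 0 to 0.60) and a narrower claim, particularly for a regimen that few patients receive.
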